### **5.2.2 Laboratory Evaluations**

Standard safety laboratory parameters collected via a local laboratory will be summarized and graded according to CTCAE Version 4.03. Lab values falling outside of a clinically accepted reference range or values that differ significantly from previous values will be evaluated for clinical significance. Abnormal laboratory findings should be considered an AE if it meets any of the following criteria: 1) causes the patient to discontinue from study treatment, 2) causes the patient to interrupt the study treatment, or 3) requires intervention.

### **5.2.3 Physical Examinations**

Physical examinations will be performed according to the schedules outlined in the latest version of the protocols. Abnormalities that were not present prior to dosing will be captured and summarized as adverse event data. Those present prior to dosing will be included as medical history.

## **5.2.4 Vital Signs**

Vital sign assessments will be performed according to the schedules outlined in the latest version of the protocol. Abnormalities will be captured as AEs only if it meets SAE criteria, cause discontinuation or interruption of study treatment, requires intervention, or deemed clinically significant based on medical judgement.

## **5.2.5 Cardiac Evaluations**

### **5.2.5.1 12-Lead Electrocardiograms**

Twelve-lead electrocardiograms (ECGs, in triplicate, approximately 1 minute apart) will be obtained according to the to the schedules outlined in the latest version of the protocol in order to evaluate the potential cardiac effects of margetuximab or prior anti-HER2 treatment, including QT interval prolongation.

### **5.2.5.2 Multigated Acquisition Ventriculography Scanning and Echocardiography**

Multigated acquisition ventriculography scanning (MUGA) scans or echocardiograms will be obtained and analyzed locally in all patients according to the schedules outlined in the latest version of the protocol. The same modality should be used throughout the study for any given patient. All MUGA scans or echocardiography performed will be evaluated for the change in LVEF from baseline.

## **5.3 Pharmacokinetic, Pharmacodynamic, and Immunological Parameter Endpoints**

PK samples and ADA samples will be collected according to the schedules outlined in the latest version of the protocol.

## **6 STATISTICAL METHODOLOGY**

### **6.1 General Considerations**

This Phase 1b/2 study is primarily observational and, thus, the majority of the statistical summaries will be descriptive. Safety and efficacy summaries will be provided for each dose level cohort and for all dose level cohorts combined. Response rates will be calculated for the response evaluable population.

Unless otherwise specified, the following general considerations are applied in data analyses:

- The baseline value is defined as the latest value prior to the start of study drugs.
- Categorical data will be summarized by the number and percent of patients falling within each category.
- Continuous variables will be summarized by descriptive statistics, including mean, standard deviation, median, minimum, and maximum.
- Time-to-event endpoints will be summarized by the number and percent of the event, median time and corresponding 95% confidence interval (CI), and event free rate and corresponding 95% CI at the specified time points of interest.
- All data summaries and tabulations will be conducted using SAS® software Version 9.3 or higher.

### **6.2 Missing Data**

Data that are reported as missing will be treated as missing in all data summaries. Incomplete dates will be imputed and defined in the Statistical Programming Plan (SPP). In descriptive summaries for safety, observations that are spurious (extreme relative to the majority of the data) will not be altered or removed from the summary.

### **6.3 Patient Disposition and Baseline Characteristics**

#### **6.3.1 Patient Disposition**

For patient disposition, the number and percentage of patients who reach various study milestones are summarized: All screened patients are broken down by screen failures (with reasons if collected) and enrolled. Then the category of enrolled is broken down by never treated (with reasons if collected) and treated. The category of treated will further be broken down by treatment ongoing and treatment discontinuation (with reasons for discontinuation, which also include protocol-defined treatment completion, if any). The end of study status for all enrolled patients will also be included. Duration of study, defined as from the date of first dose to the date of withdraw of consent, lost to follow up, death, or the last contact date, will be summarized.

### **6.3.2 Patient Demographics and Baseline Characteristics**

Patient demographics, baseline disease characteristics, disease history, medical history and other collected baseline data will be summarized using descriptive statistics.

### **6.4 Study Drug Exposures and Concomitant Medications**

Study drug exposure and concomitant medications will be summarized by descriptive statistics.

For each study drug (margetuximab and pembrolimumab), the summary of study drug exposure will include descriptive statistics as well as frequency counts for the number of doses received, the total dose administered as well as the total dose intended, and the dose intensity which is calculated as percentage of total dose administered divided by total dose intended during the period that study drug was administered. Duration of study treatment exposure will also be summarized.

The summary of concomitant medications will include the number and percentage of patients who receive any concomitant medications as well as each concomitant medication by drug class.

### **6.5 Protocol Deviations**

Major protocol deviations will be identified prior to database lock for final analysis and will be listed and summarized.

### **6.6 Efficacy Endpoint Analyses**

#### **6.6.1 Analyses of Response Endpoints**

The objective response rate (ORR) is estimated as the proportion of patients in the response evaluable population achieving a CR or PR per RECIST v1.1. A two-sided 95% exact binomial CI for ORR will be calculated. In addition, the ORR per irRECIST and its 95% CI will also be calculated.

#### **6.6.2 Analyses of Time to Event Endpoints**

##### **6.6.2.1 PFS**

The Kaplan-Meier method will be applied to estimate PFS curve, median PFS time, and PFS rates at 3 and 6 months. The method of Brookmeyer and Crowley (1) will be used to construct 95% CI for median PFS. The 95% CIs for PFS rate at 3 and 6 months will be calculated by normal approximation after log(-log) transformation.

For primary PFS analysis, the following table describes the censoring rules.

**Table 2 Censoring Rules for Primary PFS Analysis**

Situation	Date	Outcome
No baseline tumor assessments	First dose date	Censored
Death prior to first scheduled tumor assessment	Date of death	Progressed
No post-baseline tumor assessments in absence of death prior to first scheduled tumor assessment	First dose date	Censored
Documented progression	Date of progression	Progressed
Initiation of alternative anti-cancer treatments in absence of documented progression	Date of last tumor assessment prior to initiation of such treatment	Censored
Death or documented progression immediately after missing two or more consecutive scheduled tumor assessments	Date of last tumor assessment prior to missed assessments	Censored

A sensitivity analyses for PFS will be performed to assess the robustness of above primary PFS analysis. For this sensitivity analysis, the censoring rules are the same as in **Table 2** except that documented progression or death will be considered as an event, regardless when it occurs during the study.

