4.5.1 Dose Delays

Patients who experience toxicity that is potentially dose-limiting should have study drug held pending assessment, management, and resolution of the toxicity. Specific guidance for the management of known toxicities associated with pembrolizumab and margetuximab treatment, including infusion-related reactions, immune-related adverse events (irAEs), and cardiotoxicities of special interest is provided in [Section 6.5](#). For patients in whom the toxicity is assessed to be unrelated to study drug or for whom the toxicity does not meet the criteria for DLT or meet criteria for the known toxicities, therapy may be re-instituted at the same dose and schedule that was administered prior to the event, presuming the toxicity has resolved to \leq Grade 1 in severity. Reinstitution of therapy shall be conducted as follows:

- For patients in whom the toxicity is assessed to be related to study drug, dose delays of up to 14 days are allowed (see exception for cardiotoxicities of special interest described in [Section 6.5.3](#)). This may include up to one missed dose. However, the procedures at the original scheduled missed visit should be performed as soon as possible and resumed as Day 1 of next cycle with treatment reinstated after recovery from toxicity.
- For patients in whom the toxicity is assessed to be related to study drug, dose delays $>$ 14 days will result in discontinuation of treatment (see exception for cardiotoxicities of special interest described in [Section 6.5.3](#)).

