- 12 Samples will be analyzed by the local laboratory.
- 13 Includes ALB, ALK-P, ALT, AST, amylase, bicarbonate, BUN, Ca, Cl, creatinine, glucose, lipase, magnesium, phosphorus, K, Na, total protein, uric acid, total and direct bilirubin.
- 14 For Cytokine samples: Samples can be obtained selectively at additional time points in patients who experience an adverse event with signs and symptoms of cytokine release, with the goal to obtain a cytokine sample immediately at the time of onset of adverse event. Multiple cytokine samples can be drawn for any specific adverse event that is suspected to be due to cytokine release, as clinically indicated; specific date and times of blood draws must be recorded. Separate cytokine samples should be drawn for each adverse event suspected of cytokine release, with specific date and time of draw to be recorded.
- 15 Vital signs include temperature, pulse, blood pressure, and respiratory rate and are obtained as follows:
 - In relation to pembrolizumab infusions on Days 1: Vital signs will be taken immediately before the pembrolizumab infusion (up to 5 minutes before the infusion [pre-dose]); at 15 minutes after the start of infusion; at 30 minutes (end of infusion), and at 1 hour after infusion if the margetuximab dose has not already commenced.
 - In relation to margetuximab infusions on Days 1: Vital signs will be taken immediately before margetuximab infusion (up to 5 minutes before the infusion [pre-dose]), at 60 minutes after start of infusion, at 120 minutes (end of infusion), and at 1 hour after the completion of infusion.
 - Note: For subsequent cycles after Cycle 1; the 1-hour post-infusion vital signs measurements may be deferred if continuing monitoring is not clinically indicated.
- 16 Radiographic disease assessments will occur every 6 weeks (i.e., following 2 cycles of treatment) for the first 24 weeks and then every 12 weeks thereafter until documented progression, initiation of alternative anti-cancer therapy, lost to follow up, withdrawal of informed consent, death, or end of study. To be performed within 3 days prior to dosing on Day 1 of every other cycle for the first 24 weeks (specifically prior to Cycles 3, 5, 7, and 9) and then every 4th cycle (prior to Cycles 13, 17, 21, etc.). Disease assessment will be done at office follow-up visits until end of study if patient agrees.

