Appendix 5 Censoring Rules for PFS

Situation	Date	Outcome
No baseline tumor assessments	Date of first dose	Censored
Death prior to first scheduled tumor assessment	Date of death	Progressed
No post baseline tumor assessments in absence of death prior to first scheduled tumor assessment	Date of first dose	Censored
Documented disease progression	Date of disease progression	Progressed
Initiation of alternative anti-cancer treatments in absence of progression	Date of last tumor assessment prior to initiation of such treatment	Censored
Death or progression immediately after missing two or more consecutive scheduled tumor assessments	Date of last tumor assessment prior to missed assessments	Censored

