#### 5.1.2 Time to Event Endpoints

- Progression-free survival (PFS): The PFS is defined as the time from the first dose date to the date of first documented progression or death from any cause, whichever occurs first. For patients who are not known to be dead or progressed at the time of data cut-off for PFS analysis, the PFS will be censored at the date of the last tumor assessment. The documented progression is determined by radiographic assessment using RECIST v1.1. PFS will be calculated as:

$$\text{PFS (months)} = (\text{date of event [documented progression or death] or date of censoring} - \text{first dose date} + 1) / (365.25/12)$$

- Duration of response (DoR): The DoR is defined as the time from the date of initial response to the date of first documented progression or death from any cause, whichever occurs first. DoR will be analyzed for responding patients only. For responding patients who are not known to be dead or progressed at the time of data cut-off for DoR analysis, the DoR will be censored at the date of the last tumor assessment. The documented progression is determined by radiographic assessment using RECIST v1.1. DoR will be calculated as:

$$\text{DoR(months)} = (\text{date of event [documented progression or death] or date of censoring} - \text{date of initial response} + 1) / (365.25/12)$$

DoR may also be determined by irRECIST.

- Overall survival (OS): The OS is defined as the time from the first dose date to the date of death from any cause. For patients who are not known to be dead at the time of data cut-off for OS analysis, the OS will be censored at the time they are last known to be alive. OS will be calculated as:

$$\text{OS (months)} = (\text{date of death or last known alive} - \text{first dose date} + 1) / (365.25/12)$$

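### Read literally, the PFS censoring table censors at first dose an unscanned patient who dies between the first and second scheduled scans, which slightly overstates the primary 3- and 6-month PFS rates

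*SAP*

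**What the plan says.** SAP 5.1.2 defines PFS as "the time from the first dose date to the date of first documented progression or death from any cause, whichever occurs first". It reserves censoring at the last tumor assessment for "patients who are not known to be dead or progressed at the time of data cut-off for PFS analysis".

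SAP Table 2 sets the censoring rules for the primary PFS analysis. Three of its six rows matter here:

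- Row 2: a death before the first scheduled assessment is an event at the date of death.
- Row 3: "No post-baseline tumor assessments in absence of death prior to first scheduled tumor assessment" is censored at the first dose date.
- Row 6: "Death or documented progression immediately after missing two or more consecutive scheduled tumor assessments" is censored at the last assessment before the gap.

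Protocol Appendix 5 has the same rows; its row 3 reads "No post baseline tumor assessments in absence of death prior to first scheduled tumor assessment". Neither table has a general row for death without documented progression.

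The SAP plans one sensitivity analysis, which keeps Table 2 except that "documented progression or death will be considered as an event, regardless when it occurs during the study".

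Scans are due about every 6 weeks for the first 24 weeks. Footnote 16 of protocol Appendix 2 ties them to dosing: "To be performed within 3 days prior to dosing on Day 1 of every other cycle for the first 24 weeks".

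**The concern.** Row 3 names one exception, a death before the first scheduled scan. A treated patient who misses that scan and dies before the second falls outside the exception and is censored at time zero. That conflicts with the PFS definition, and it discards a death after one missed scan where row 6 requires two.

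These patients are in the analysis, because the Safety Population used for PFS needs only one dose. Those who deteriorate too fast to be scanned are plausibly the ones who die early. Removing them from the risk set before any event can only raise the landmark PFS rates.

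**Working it through.** **1. Apply the rows.** Take a patient with no post-baseline scan and no other anti-cancer therapy, with scans due at Weeks 6, 12, 18 and 24.

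| Death at | Scans missed | Rows that match | Result |
|---|---|---|---|
| Week 4 or 5.9 | 0 | 2 | Event at death |
| Week 8 or 11.9 | 1 | 3 only | Censored at first dose |
| Week 13 or 20 | 2 or 3 | 3 and 6 | Censored |

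The middle line is the problem. The nominal window is Days 42 to 84, before the 3-month landmark (3 × 365.25/12 = 91.3 days).

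**2. Formula.** The plan gives no figure to reproduce. A patient censored at first dose leaves the risk set before any event. With k such patients among N, and x progression-free at the landmark, the rate is x/N with the deaths counted and x/(N − k) under row 3. With f = k/N and S the rate under row 3, the overstatement is S − (1 − f)S = f × S. Example: N = 30, x = 12, k = 1 gives 40.0% against 41.4%.

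**3. Inputs.** The documents do not give f; I assume 2% and 5%. For median PFS m in the remaining patients I assume 1.9 months (protocol 2.2.1, pembrolizumab monotherapy) to 2.6 months (protocol 2.1.2, weekly paclitaxel), with exponential progression times. A month is 30.4375 days. Progression seen by 3 months has occurred by Day 84; by 6 months, by Day 168. So S = exp(−ln2 × t/(30.4375m)), with t = 84 or 168.

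| m (months) | S at 3 mo | f × S: 2%; 5% | S at 6 mo | f × S: 2%; 5% |
|---|---|---|---|---|
| 1.9 | 36.5% | 0.73; 1.83 points | 13.4% | 0.27; 0.67 points |
| 2.6 | 47.9% | 0.96; 2.40 points | 23.0% | 0.46; 1.15 points |

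At m = 2.6 and f = 5%, the reported 3-month rate is 47.9%, against 0.95 × 47.9 = 45.5% with the deaths counted. In counts, at 3 months: 1, 2 or 4 such deaths among 85 expansion patients add 0.43–0.56, 0.86–1.13 or 1.72–2.25 points; 1 among 30 in a region adds 1.22–1.60.

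A simulated Kaplan-Meier check (100,000 patients per scenario) agrees to within about 0.01 point.

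**4. Plausibility of f.** On the nominal schedule, all deaths in Weeks 6 to 12, scanned or not, are D = exp(−ln2 × 42/(30.4375 × OS)) − exp(−ln2 × 84/(30.4375 × OS)). For OS medians quoted in the protocol, D is 14.4% (5.0 months), 10.2% (7.8) or 7.4% (11.4). So f = 2% needs 14% to 27% of those deaths to be unscanned, and f = 5% needs 35% to 68%.

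**5. Delayed scans.** Protocol 4.5.1 says that for related toxicity "dose delays of up to 14 days are allowed". If every scan slips 14 days, the window is Days 56 to 98. With deaths spread evenly, 7/42 = 1/6 of them fall after Day 91, so the 3-month overstatement is f × (S(56) − 1/6), with S(56) = 51.1% or 61.2%. That gives 0.69–0.89 points at 2% and 1.72–2.23 at 5%. This is an illustration, not a bound: protocol 6.8 allows up to 4 weeks for palliative radiotherapy, and protocol 6.3 sets no limit for reasons unrelated to study therapy.

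**6. Median.** In the scenarios of step 3 the median is the Week 12 scan (85/30.4375 = 2.79 months) under both rules. It need not be. At an assumed m = 2.8, the Week 12 rate is 50.5% under row 3 and 0.95 × 50.5 = 48.0% with f = 5% counted, so the median moves from the Week 18 scan to the Week 12 scan.

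**7. Scale.** Near a 45% rate the 95% half-width, 1.96 × √(0.45 × 0.55/N), is 10.6 points at N = 85 and 17.8 at N = 30.

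**The case against.** The strongest reply is that Table 2 was never a closed list. A patient with a clean Week 6 scan who dies at Week 10 matches no row, and that death is an event only through the definitions in SAP 5.1.2 and protocol 9.5. If the table must be read with the definition, row 3 can be taken as supplying a date for patients without an event. Nor does a clash with the definition settle the matter, since row 6 censors known deaths on purpose.

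That reading is possible, but row 3 does not state it. Its single exception implies that later deaths are not excepted, and two programmers could code it differently.

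Other points stand in part:

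- The sensitivity analysis counts these deaths. It also lifts the two-missed-scan rule, so it does not isolate this effect, and the primary rates stay as they are.
- PFS is a secondary, descriptive endpoint, and no test or decision rests on the landmark rates. This stands and limits the weight of the point.
- The frequency is unknown. A CT/MRI is marked at the End of Treatment visit, and any such scan takes the patient out of row 3, although protocol 8.3 makes that visit optional.
- Off treatment, protocol 4.1.4 describes 12-week follow-up intervals, so the edges of the window are uncertain for a patient who stops early.

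A reader might infer that early deaths are hidden altogether, or that the trial's main efficacy result is inflated. The documents support neither: OS and the sensitivity analysis both count these deaths, and ORR does not use this table.

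**Conclusion.** The wording is wrong as written and should be corrected; the effect is small. Under the assumed f and median PFS, the primary PFS rates are overstated by 0.73 to 2.40 points at 3 months and 0.27 to 1.15 at 6 months. The direction follows from the rule; the size rests on assumptions, because no document reports how many patients die unscanned in the window.

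The median is unchanged in those scenarios but could shift by one scan if the Week 12 rate is just above 50%, so neither a general claim that it is biased nor one that it is immune is supported. ORR, OS and the response-based futility rule do not use the table. Duration of response uses it, but responders have post-baseline scans, so row 3 cannot apply to them.

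**What to change.** In both SAP Table 2 and protocol Appendix 5:

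- Keep row 2 and the two-missed-assessments row unchanged.
- Add one general row: *Death without documented progression, not after two or more consecutive missed scheduled assessments and with no prior alternative anti-cancer therapy: date of death, event.* This also covers the ordinary death that now matches no row.
- Reword row 3: *No post-baseline tumor assessment and no death counted as an event under the rows above: first dose date, censored.*
- Do not let the alternative-therapy row override row 2.

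The cost is one added and one reworded row in each document. The study is open-label, and protocol 2.3.1.1 reports 64 patients treated by 30 September 2017, so the change should be dated before database lock and the result under the current wording shown alongside. The downside is slightly less favourable 3- and 6-month PFS rates.

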### 6.6.2.2 DoR

The Kaplan-Meier method will be applied to estimate DoR curve, median DoR time, and DoR rates at 3 and 6 months. The same censoring rules as in **Table 2** will be applied. The method of Brookmeyer and Crowley (1) will be used to construct 95% CI for median DoR. The 95% CIs for DoR rate at 3 and 6 months will be calculated by normal approximation after log(-log) transformation. These analyses will also be repeated for DoR based on irRECIST.

### 6.6.2.3 OS

The Kaplan-Meier method will be applied to estimate OS curve, median OS time, and OS rates at 1 and 2 years. The method of Brookmeyer and Crowley (1) will be used to construct 95% CI for median OS. The 95% CIs for OS rate at 1 and 2 years will be calculated by normal approximation after log(-log) transformation.

### 6.6.3 Tumor Size Change Over Time

Change in tumor size, measured as the sum of target lesions measurements, from baseline over time will be summarized as well as presented by spider plot. The best percentage change from baseline will be presented by waterfall plot.

